7.4 Follow-up Procedures

Subjects will come back for a 1st visit after the screening visit; 2nd visit at 45 days (\pm 1 week) following the first visit, and 3rd visit following 90 days after the first visit (\pm 2 weeks). All of the procedures done at the baseline visit will be done in the 2nd and 3rd visits (see flowchart).

In addition, subjects will be asked about their usage of the ITN. Ocular safety and tolerability questionnaire (appendix VI) will be administered in the 2nd and 3rd visit. The subject will be asked to complete a diary every day to record any pain symptoms (Appendix VII). The subject will be asked to send their pain diary weekly to the study coordinator, in however method works for the subject to ensure compliance with the ITN. They will also need to bring the diary to each study visit, to ensure compliance.

Ocular Tolerability Questionnaire (Appendix VI): This questionnaire assesses tolerability of the ITN device. It assesses symptoms of discomfort in each eye after ITN use.

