7.6 Early Termination

If a subject withdraws or is withdrawn from the study prior to completion of all study visits, there will be no additional procedures performed

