8. SAFETY AND EFFECTIVENESS ASSESSMENTS

8.1 Safety Assessments

The primary safety variable monitored will be the occurrence of adverse events. The severity of each adverse event observed will be evaluated as serious or not serious and the occurrence will be evaluated as expected or unexpected. The relationship of the event to the study medication will be assessed by the investigator as possibly, probably, or definitely related. Safety variables will be evaluated at all study visits. If adverse events occur, the first concern will be the safety of the study participants. Any serious adverse event occurring during the study period will be immediately reported to TUFTS IRB. At each visit throughout the study, the investigator will begin querying for adverse events by asking each subject a general, non-directed question such as "How have you been feeling since the last visit?" or "How have your eyes been since the last visit?"

A comprehensive eye examination including best-corrected visual acuity, evaluation of the condition of conjunctiva, cornea, anterior chamber, iris/pupil, lens, will be performed.

Withdrawal from the study will happen if any of the following occurs:

- Investigator determination that it is not in the best interest of the subject to continue participation.
- Subject's wish to withdraw for any reason.

After being withdrawn, subjects will be followed according to each case until the adverse event is resolved.

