Research subjects will be routinely questioned about adverse events at study visits. All observed or volunteered adverse events (serious or non-serious) and abnormal test findings, regardless of study group or suspected causal relationship to the study device(s) will be recorded in the subjects' case histories (source data, case report form). For all adverse events, sufficient information will be pursued and/or obtained so as to permit 1) an adequate determination of the outcome of the event (i.e., whether the event should be classified as a serious adverse event) and; 2) an assessment of the causal relationship between the adverse event and the study device.

Tufts Medical Center

Adverse events or abnormal test findings thought to be associated with the study device (ITN) will be followed until the event (or its sequel) or the abnormal test finding resolves or stabilizes at a level acceptable to the Investigator.

An abnormal test finding will be classified as an adverse event if one or more of the following criteria are met:

- The test finding is accompanied by clinical symptoms
- The test finding necessitates additional diagnostic evaluation(s) or medical/surgical intervention; including significant additional concomitant drug treatment or other therapy
- The test finding is considered an adverse event by the Investigator. Note: simply repeating a test finding, in the absence of any of the other listed criteria, does not constitute an adverse event.

The Investigator will promptly review documented adverse events and abnormal test findings to determine 1) if the abnormal test finding should be classified as an adverse event; 2) if there is a reasonable possibility that the adverse event was caused by the study device; and 3) if the adverse event meets the criteria for a serious adverse event.

If the Investigator's final determination of causality is "unknown and of questionable relationship to the study device", the adverse event will be classified as associated with the use of the study device for reporting purposes. If the Investigator's final determination of causality is "unknown but not related to the study device", this determination and the rationale for the determination will be documented in the respective subject's case history (source data or case report form).

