9.3 Withdrawal of Subjects due to Adverse Events

Withdrawal from the study will happen if any of the following occurs:

- Investigator determines that is not in the best interest of the subject to continue participation.
- Subject's wishing to withdraw for any reason.

Tufts Medical Center

After being withdrawn, subjects will be followed according to each case until the adverse event is resolved.

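### Once home use begins, adverse events are actively asked about only at visits up to 66 days apart, with no query planned at withdrawal, so nasal and withdrawal-related events may be missed unless volunteered

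*Combined protocol and SAP*

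**What the plan says.** Aim 2 (section 2.0) includes safety over 90 days of daily use. Section 10.2 lists safety and tolerability as secondary outcomes, and 8.1 and 10.6 name the occurrence of adverse events as the primary safety variable.

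- **Active questioning.** Section 8.1: "At each visit throughout the study, the investigator will begin querying for adverse events by asking each subject a general, non-directed question". Section 9.1: "Research subjects will be routinely questioned about adverse events at study visits". The open question is only the start. Section 10.6 adds directed questioning on tolerability, 7.4 (Follow-up Procedures) gives the Appendix VI form at visits 2 and 3, and 8.1 requires an eye examination.
- **Schedule.** Section 7.4 (Follow-up Procedures): "2nd visit at 45 days (\pm 1 week) following the first visit" and "3rd visit following 90 days after the first visit (\pm 2 weeks". Section 5.3 sets a minimum of two uses a day.
- **Between visits.** Under 9.1, "All observed or volunteered adverse events (serious or non-serious) and abnormal test findings" are to be recorded. Section 7.5 requires an adverse-event review if the patient attends the cornea clinic for another reason. Section 7.4 also says "The subject will be asked to send their pain diary weekly to the study coordinator", and gives compliance as the purpose.
- **Withdrawal.** Section 7.6: "there will be no additional procedures performed". Sections 8.1 and 9.3: "subjects will be followed according to each case until the adverse event is resolved". Section 5.2 allows withdrawn patients to be replaced, and 10.4 defines no analysis population.

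**The concern.** The trial has one arm, so its safety result is the adverse-event count itself, and no comparator would reveal incomplete ascertainment. A question that is not asked can lose events but cannot add them, so any error of this kind favours the device.

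Two groups of events are exposed. The first is nasal and other non-ocular events. The device acts in the nose, and 4.2 excludes patients with nosebleeds, nasal surgery or severe nasal obstruction. Yet Appendix VI grades three eye symptoms and adds one open item, worded around the study tests. A minor nasal effect during home use therefore depends on the general question weeks later, or on the patient volunteering it. The second is events in patients who withdraw. Someone who stops because of the device plausibly had an event, and no planned step asks. A continuing problem may also be recognised late.

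**Working it through.** The plan states no maximum interval and no event rate, so there is no figure of its own to reproduce. The check is date arithmetic on the windows in 7.4 (Follow-up Procedures), followed by a comparison of the withdrawal sections.

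**1. Windows, in days after the first visit**
- Visit 2: 45 − 7 = 38 to 45 + 7 = 52.
- Visit 3: 90 − 14 = 76 to 90 + 14 = 104.

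**2. Interval between visit 2 and visit 3**
- Longest: 104 − 38 = 66 days. Nominal: 90 − 45 = 45. Shortest: 76 − 52 = 24.
- Section 7.2 also describes the visits as 6 weeks ± 1 week and 3 months ± 2 weeks. With 42 days, and 90 to 92 days assumed for three months, the longest interval is (90 + 14) − 35 = 69 to (92 + 14) − 35 = 71 days.

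**3. Home use before the first query that can cover it**
- Visit 2 falls on days 38 to 52. A patient whose visit 2 is due on day 52 and who leaves the day before has 51 days of use. At the minimum of two sessions a day, that is 51 × 2 = 102 sessions.
- A patient who leaves between days 38 and 51 may already have attended visit 2, so 51 days is a maximum and not typical.

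**4. Weekly contact**
- A symptom line in the weekly diary return would cut the longest interval from 66 to about 7 days (66 / 7 = 9.4 times shorter). It would give about 6 contacts by day 45 (45 / 7 = 6.4).

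**5. Withdrawal sections side by side**
- Section 7.6 ends procedures at withdrawal. Sections 8.1 and 9.3 continue follow-up until the adverse event resolves. The second needs an event that someone already knows of, and neither creates a step that finds one.

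**6. Illustration of size; all event rates are assumed**
- Section 10.3 inflates 25 to 30, an implied dropout of 5/30 = 16.7%. (Section 3.1 gives 45 patients; the same share gives the same percentages.)
- Suppose 10% of completers have an event, a share p of dropouts do, and none of the dropouts' events is captured. Share missed = 5p / (25 × 0.10 + 5p).

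| p | Expected patients with an event | Captured | Share missed |
|---|---|---|---|
| 10% | 2.5 + 0.5 = 3.0 | 2.5 | 17% |
| 30% | 2.5 + 1.5 = 4.0 | 2.5 | 38% |
| 50% | 2.5 + 2.5 = 5.0 | 2.5 | 50% |

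These are upper bounds, because volunteered events and any visit before withdrawal would capture some. The denominator matters as well. The 2.5 captured give 2.5/25 = 10% if dropouts are left out and 2.5/30 = 8.3% if they are kept in unasked, against true values of 10%, 13.3% and 16.7%.

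**The case against.** The strongest reply is that the plan collects more than one open question at two visits. At visits 2 and 3 the open question is joined by directed tolerability questioning, Appendix VI and an eye examination, and abnormal findings can be classed as adverse events under 9.1. Between visits, volunteered events are recorded, and a patient in weekly contact with the coordinator has an easy route to report one. The daily diary already records discomfort, pain and photosensitivity around each use, and its OPAS page covers redness, burning, light sensitivity and tearing. Ocular flares therefore do not depend on six to nine weeks of recall. Visit-based questioning is also a common choice in a small pilot of a device that section 1.1 describes as FDA-approved.

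All of that stands, and it narrows the point to non-ocular events and to withdrawals. It does not close either gap: Appendix VI is given only at visits 2 and 3, the diary's stated use is compliance, and its readable pages have no adverse-event or nasal item.

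A reader might infer that harms will be under-counted. The documents give no event, withdrawal or recall rate, so only *may be* is supportable. A reader might also infer that withdrawn patients get no safety follow-up, but 8.1 and 9.3 do follow a known event. Nor does the one-week rule for informing the principal investigator in 11.1 conflict with the visit interval, since it does not say when the week starts.

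**Conclusion.** The gap is real but limited. After home use starts, active adverse-event questioning is planned only at day 38–52 and day 76–104, at most 66 days apart and nominally 45. No query at withdrawal appears in the readable text, which leaves up to about 51 days (102 sessions) of use uncovered in a patient who leaves before visit 2. The events at risk are mainly nasal and other non-ocular ones, and those in patients who withdraw. The size of any loss is unknown.

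This rests on the windows in 7.4 (those in 7.2 give 69 to 71 days), on the minimum use in 5.3, and on the readable text. The flowchart cited in 7.2 and 7.4 is not available, and Appendix VII shows sample pages with missing figures, so an item there could alter the statements of absence. Sections 7.6, 8.1 and 9.3 need reconciling in any case. The change should be made because safety is part of Aim 2 and the means of contact already exist.

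**What to change.** 1. Change 7.6 so that every withdrawal includes one adverse-event query and the Appendix VI form at last contact; a telephone call suffices. Reconcile 7.6 with the follow-up promised in 8.1 and 9.3.
2. Add one yes/no line to the weekly diary return asking about any new or worse symptom in the eye, nose or elsewhere, with space to describe it. State in 7.4 (Follow-up Procedures) and 8.1 that the coordinator passes any *yes* to the treating investigator.
3. State in 10.4 and 10.6 that every patient who used the device, including those withdrawn and replaced, stays in the adverse-event denominator. This belongs with item 1: keeping patients in the denominator without asking them lowers the reported rate.

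The cost is one diary line, one call per withdrawal, a little coordinator time and a few sentences of protocol text. The reported event rate will probably be somewhat higher, and the report should say that events were asked about weekly. No visit is added.

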9. ADVERSE EVENT RECORDING AND REPORTING

9.1 Recording Requirements

Adverse Events (AEs)

An adverse event is any untoward medical occurrence in a clinical investigation subject administered a pharmaceutical product, regardless of causal attribution.

Serious Adverse Events (SAEs)

A serious adverse event is any adverse event that meets any of the following criteria:

- Is fatal (i.e., the adverse event actually causes or leads to death)
- Is life threatening (i.e., the adverse event, in the view of the investigator, places the patient at immediate risk of death)

Unanticipated Problems

According to the Office of Human Research Protections (OHRP), unanticipated problems includes “any incident, experience, or outcome that meets all of the following criteria:

1. unexpected (in terms of nature, severity, or frequency) given (a) the research procedures that are described in the protocol-related documents, such as the IRB-approved research protocol and informed consent document; and (b) the characteristics of the subject population being studied;
2. related or possibly related to participation in the research (in this guidance document, possibly related means there is a reasonable possibility that the incident, experience, or outcome may have been caused by the procedures involved in the research); and
3. suggests that the research places subjects or others at a greater risk of harm (including physical, psychological, economic, or social harm) than was previously known or recognized.

Unanticipated Adverse Device Effect (UADE)

Unanticipated adverse device effect means any serious adverse effect on health or safety or any life-threatening problem or death caused by, or associated with, a device, if that effect, problem, or death was not previously identified in nature, severity, or degree of incidence in the investigational plan or application (including a supplementary plan or application), or any other unanticipated serious problem associated with a device that relates to the rights, safety, or welfare of subjects.

Research subjects will be routinely questioned about adverse events at study visits. All observed or volunteered adverse events (serious or non-serious) and abnormal test findings, regardless of study group or suspected causal relationship to the study device(s) will be recorded in the subjects' case histories (source data, case report form). For all adverse events, sufficient information will be pursued and/or obtained so as to permit 1) an adequate determination of the outcome of the event (i.e., whether the event should be classified as a serious adverse event) and; 2) an assessment of the causal relationship between the adverse event and the study device.

Tufts Medical Center

Adverse events or abnormal test findings thought to be associated with the study device (ITN) will be followed until the event (or its sequel) or the abnormal test finding resolves or stabilizes at a level acceptable to the Investigator.

An abnormal test finding will be classified as an adverse event if one or more of the following criteria are met:

- The test finding is accompanied by clinical symptoms
- The test finding necessitates additional diagnostic evaluation(s) or medical/surgical intervention; including significant additional concomitant drug treatment or other therapy
- The test finding is considered an adverse event by the Investigator. Note: simply repeating a test finding, in the absence of any of the other listed criteria, does not constitute an adverse event.

The Investigator will promptly review documented adverse events and abnormal test findings to determine 1) if the abnormal test finding should be classified as an adverse event; 2) if there is a reasonable possibility that the adverse event was caused by the study device; and 3) if the adverse event meets the criteria for a serious adverse event.

If the Investigator's final determination of causality is "unknown and of questionable relationship to the study device", the adverse event will be classified as associated with the use of the study device for reporting purposes. If the Investigator's final determination of causality is "unknown but not related to the study device", this determination and the rationale for the determination will be documented in the respective subject's case history (source data or case report form).

9.2 REPORTING PROCEDURES

➤ REPORTING OF ADVERSE EVENTS TO FDA

Unanticipated Adverse Device Effect (UADE) will be reported to the sponsor and the IRB within 5 business days after investigators first learns of the event.

Reporting Adverse Events to Other External Entities

Therefore no reports on adverse events will be submitted to external entities.

➤ Reporting Adverse Events to the Human Studies Committee

TUFTS policy for "REPORTING ADVERSE EVENTS AND UNANTICIPATED PROBLEMS" will be followed.

9.3 Withdrawal of Subjects due to Adverse Events

Withdrawal from the study will happen if any of the following occurs:

- Investigator determines that is not in the best interest of the subject to continue participation.
- Subject's wishing to withdraw for any reason.

Tufts Medical Center

After being withdrawn, subjects will be followed according to each case until the adverse event is resolved.

10. STATISTICAL METHODS/DATA ANALYSIS

10.1 Primary endpoint(s) or outcome measure(s)

- Change to overall pain by the Visual Analogue Scale (VAS) after ITN stimulation

10.2 Secondary Outcome Measures:

- Change to overall pain by the Visual Analogue Scale (VAS) after daily ITN stimulation over 45-day period.
- Change to overall pain by the Visual Analogue Scale (VAS) after daily ITN stimulation over 90-day period.
- Change in quality of life as measured daily with OPAS and IDEEL
- Safety
- Tolerability
- Change in response to hypertonic solution
- Change in response to proparacaine challenge test
- Change in the intraocular pressure (IOP) measured in each visit.
- Reduction on other concomitant pain therapy

10.3 Sample Size Determination:

There is no existing systematic epidemiological study regarding the neuropathic corneal pain and there are no studies available to determine the population sample needed to detect differences between patients before and after the neuro stimulation for neuropathic corneal pain. However, based on a recent preliminary observations in 5 patients with concurrent NCP and dry eye disease, and the decrease in pain levels immediately after the use of ITN, we would achieve 80% power with an alpha error of 0.05 for pain scale intensity of 1-10, and assumption of 50% decrease in pain levels, for a sample size of 25 patients. The enrollment of 30 patients with NCP would compensate for potential dropouts.

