3.0 STUDY DESIGN

3.1. Study Design Description

This study is a prospective, interventional, open-label, single arm, non-randomized trial treating 45 patients with peripheral or mixed neuropathic corneal pain at their baseline exam and following 45 days and 90 days of daily use with the TrueTear™ ITN device.

3.2 Statistical analysis:

Two-tailed paired sample t-test and Pearson correlation will be performed for pain intensity, and to assess associations between different quality of life scores. Statistical comparisons of the mean values between different groups based will be performed using ANOVA.

The normality of continuous variables will be tested with the Shapiro-Wilk test. All tests will be two tailed and statistical significance will be considered for p values of less than 0.05.

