5.2 Study Device Compliance/Adherence

Directed questioning using the (Ocular Tolerability and Compliance Questionnaire – Appendix VI) will be administered by the investigator or research staff. Results on the participants' compliance and adherence to the study protocol and study device will be recorded on the paper case report form (CRF). During the study, all concomitant medication treatment regimens, ocular hygiene treatments (i.e., lid scrubs and warm compresses), or insertion of punctal plugs will be kept constant as permitted by accepted medical practice. If one of the aforementioned treatment regimens needs to be modified, the participant may be withdrawn based on the investigator's discretion.

Participants must be compliant with IVCM imaging on the study visit or they will be withdrawn. Subjects who are withdrawn may be replaced by new enrolled subjects to maintain the sample size.

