10.4 Analysis Population

N/A

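### The sample size is internally inconsistent: section 3.1 treats 45 patients, section 10.3 enrols 30 to keep 25, and section 5.2 allows replacement up to an unnamed number

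*Combined protocol and SAP*

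**What the plan says.** Three sections of the combined protocol and SAP bear on the number of patients.

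- **Section 3.1, Study Design Description:** a "single arm, non-randomized trial treating 45 patients with peripheral or mixed neuropathic corneal pain", seen at baseline and after 45 and 90 days of daily device use.
- **Section 10.3, Sample Size Determination:** "we would achieve 80% power with an alpha error of 0.05 for pain scale intensity of 1-10", assuming a 50% fall in pain, "for a sample size of 25 patients. The enrollment of 30 patients with NCP would compensate for potential dropouts". The stated basis is preliminary observation of five patients immediately after device use.
- **Section 5.2, Study Device Compliance/Adherence:** "Subjects who are withdrawn may be replaced by new enrolled subjects to maintain the sample size". Replacement is optional, and no target or cap is given. The same section provides for withdrawal of participants who do not comply with confocal imaging.

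Section 10.4, Analysis Population, is marked not applicable, so it does not link the numbers either. Section 10.1 makes the primary endpoint the change in VAS pain after stimulation. Section 10.2 lists the 45-day and 90-day changes separately as secondary. Section 7.2 places in-office testing of the device, and the response to it, at the first visit.

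**The concern.** Sections 3.1 and 10.3 give different sizes for the same single-arm trial. Neither refers to the other, and no section explains where 45 comes from.

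The replacement rule turns this into a practical problem. Staff applying section 5.2 need to know which number they are restoring: 25, 30 or 45. The 30 already contains an allowance for dropouts, so replacing withdrawals as well could cover the same losses twice. The protocol does not say whether that is intended.

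At stake is whether a reader can tell when recruitment is complete. A trial that stopped at 30 and one that stopped at 45 could each be described as following the protocol. The reader also cannot tell which evaluable number the 80% power describes.

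**Working it through.** **Inputs from the document**

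| Input | Value | Source |
|---|---|---|
| Number treated | 45 | 3.1 |
| Number for 80% power | 25 | 10.3 |
| Number enrolled | 30 | 10.3 |
| Dropout rate | not stated | 10.3 |
| Number that replacement maintains | not stated | 5.2 |
| Test and alpha | paired t-test, two-sided 0.05 | 3.2, 10.3 |
| Effect | 50% fall in pain; baseline mean not stated | 10.3 |
| SD of the change | not stated | 10.3 |

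**Step 1. Can the 25 be reproduced?** No, and it cannot be refuted. Without a baseline mean, the 50% fall cannot be turned into points; without the SD of the change, points cannot be turned into a sample size. The answer depends heavily on what is assumed:

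- baseline 4 points, so a change of 2: an SD of change from 2 to 5 gives n = 10 to 52;
- baseline 6 points, so a change of 3: the same SDs give n = 6 to 24.

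These baselines and SDs are my assumptions.

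**Step 2. Does 25 lead to 30?** Yes. (30 − 25)/30 = 16.7% loss. Alternatively, 25 × 1.20 = 30. The document states neither rate, but the step is coherent.

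**Step 3. Does either figure lead to 45?** Not with any stated rate.

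- From 45 down to 25: (45 − 25)/45 = 44.4% loss.
- From 45 down to 30: (45 − 30)/45 = 33.3% loss.
- Enrolment against enrolment: 45 − 30 = 15 patients, and 15/30 = 50% more. That is too large for rounding.

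**Step 4. How much does the choice matter for power?** For a paired t-test with standardised effect d (mean change divided by SD of the change), power is the probability that a noncentral t variable with n − 1 degrees of freedom and noncentrality d√n exceeds the two-sided 5% critical value. Take the plan's 80% at n = 25 as correct and solve for d. The result is d = 0.584; the normal approximation gives (1.960 + 0.842)/√25 = 0.560. Hold d at 0.584 and vary n:

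| Evaluable n | d√n | Power at d = 0.584 | d detectable with 80% power |
|---|---|---|---|
| 25 | 0.584 × √25 = 2.92 | 80.0% | 0.584 |
| 30 | 0.584 × √30 = 3.20 | 87.1% | 0.529 |
| 45 | 0.584 × √45 = 3.92 | 96.9% | 0.427 |

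Between 30 and 45 evaluable, the detectable effect falls by 1 − 0.427/0.529 = 19.3%. The value 0.584 is solved backwards from the plan's own claim. It shows scale and does not support the 80%.

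**The case against.** The strongest case on the other side has three parts.

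**The conflict is harmless.** This is an open-label, single-arm pilot with no interim analysis. Section 10.3 says that 30 would be enough to cover dropouts, and 45 is also enough. This stands as far as power goes. A reader might infer from three conflicting numbers that the trial is underpowered, and the document does not support that, because both enrolment figures exceed 25. But nothing confirms that 30 was meant as a minimum and 45 as the plan, so a reconciling statement is still needed.

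**Dropout hardly touches the primary endpoint.** The power basis in 10.3 is the fall in pain immediately after use, and the device is tested in the office at the first visit. Losses over the following 90 days would mainly affect the secondary 45-day and 90-day changes. This stands. It would be tempting to apply the 16.7% loss to 45 and say that about 37 would be evaluable for the primary endpoint, but no section gives that rate or that number. The number evaluable for an immediate endpoint may be close to the number treated.

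**Other gaps are different in kind.** The missing baseline mean and SD, and the undefined analysis population, are missing detail and not contradictions. This also stands. A reader might infer from the missing inputs that the 25 is wrong; they show only that it cannot be checked. Nor is this an arithmetic error, since the step from 25 to 30 works.

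**Conclusion.** The inconsistency is real and stands in the current text. Sections 3.1 and 10.3 give enrolment figures that differ by 15 patients, at least one of them must be changed or explained, and section 5.2 depends on a number it does not name. Because the trial's size is affected and the repair is cheap, it should be corrected.

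The consequence is an undetermined recruitment target and a power statement not tied to a definite number; no loss of power is shown. The figures of about 87% at 30 and 97% at 45 rest on three assumptions: that the stated 80% at 25 is right, that the primary test is the two-sided paired t-test of section 3.2, and that all 30 or all 45 patients are evaluable. The document does not settle which enrolment figure was intended.

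**What to change.** 1. State one intended enrolment number, the same in 3.1 and 10.3.
2. In 5.2, name that number as the one replacement maintains.
3. In 10.3, state the number expected to be evaluable for the immediate primary endpoint, the dropout rate the sponsor itself assumes, whether replacement is in addition to that allowance, and the power restated for that evaluable number.

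The 16.7% loss, a figure of 37 evaluable and the back-solved effect of 0.58 SD should not be written into the protocol. They are illustrations derived from the plan's own figures and have no independent basis.

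As lesser matters, 10.4 could define who counts as evaluable for the primary endpoint, and 10.3 could report the baseline mean and SD of change from the five preliminary patients, or say that they are not available.

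The cost is wording in 3.1, 5.2 and 10.3, with 10.4 optional. The real downside is that the sponsor must choose between 30 and 45. If the choice differs from the number now in use, the recruitment target moves by up to 15 patients.
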